Pan-HER Infusion		X		X	X	X	X	X	X	X		X	X	X	X		
Post-Infusion Monitoring		X		X	X	X	X	X	X	X		X	X	X	X		

Abbreviations (in alphabetical order): ADA, anti-drug antibody; C, Cycle; CT, computed tomography; D/d, day(s); DLT, dose-limiting toxicity; EOT, End of Treatment; ECG, electrocardiogram; ECHO, echocardiogram; ECOG PS, Eastern Cooperative Oncology Group performance status; MRI, magnetic resonance imaging; MUGA, multi-gated acquisition; 1M FUP, 1-Month Follow-up; PK, pharmacokinetic; (S)AE, (serious) adverse event

Confidential Page 43 of 156

- 1) The treatment period continues until the patient is withdrawn from Pan-HER.
- 2) Applicable for Part 2 only: After the 1M FUP Visit, the Investigator will make every effort to obtain follow-up information on response assessment and/or OS every 2 months. Response assessment follow-up is required in the event of an ongoing SD, PR or CR at the 1M FUP Visit, until PD or another therapeutic intervention is initiated. Survival follow-up is required until death, withdrawal of consent, or termination of the trial. This continued follow-up does not require an in-person visit at the trial site, but may be obtained by collection of data/documentation.
- 3) Informed consent may be obtained outside the 14-day screening period prior to C1/D1, but is recommended to be obtained no earlier than 4 weeks prior to the planned C1/D1.
- 4) Screening assessments/baseline characteristics include demographics, medical history, tumor histology, mutation status, extent of disease, prior anti-cancer treatment etc.
- 5) DLT evaluation, Applicable for Part 1 only: DLTs are reported during Cycle 1 with final assessment 7 days after the last dose of Cycle 1 or prior to dosing on C2/D1.
- 6) Does not need to be performed on C1/D1 if performed during screening ≤ 7 days from C1/D1.
- 7) In addition to the scheduled timepoints, an ECG should be performed in the event of cardiac symptoms.
- 8) In addition to the scheduled timepoints, an ECHO/MUGA should be performed in the event of cardiac symptoms.
- 9) Local laboratory results must be available and assessed prior to each Pan-HER infusion for all infusions during Cycle 1, and for every second infusion from Cycle 2 onwards. Refer to Section 8.2.9 for further details
- 10) Complement sampling, Applicable for Part 2 only, will be done C1/D1 and in the event of an IRR. Refer to Section 8.2.10 for further details.
- 11) CT or MRI imaging schedule and conditions, applying to all cohorts:

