7.2 Other Drugs to be Used in the Trial

7.2.1 Pre-Medication for Pan-HER Infusion-Related Reactions

There is an inherent risk for IRRs with the administration of mAbs. A premedication schedule will therefore be implemented for all patients treated.

For Part 1, premedication is mandatory prior to each dose of Pan-HER.

For Part 2, premedication is mandatory prior to each dose of Pan-HER during Cycle 1 and 2.

As of Amendment 5, all patients must be premedicated as described with standard therapies that include each of the following. The recommended premedication doses are as follows:

- Montelukast (selective leukotriene receptor antagonist) 10 mg PO daily × 7 prior to each Pan-HER infusion (schedule may be extended to daily throughout study at the Investigator's discretion); plus approx. 0.5 hours prior to the start of Pan-HER infusion
- Dexamethasone 10 mg PO, approx. 12 and 6 hours prior to the start of Pan-HER infusion
- Glucocorticoid therapy equivalent to 80-100 mg IV methylprednisolone, approx. 0.5 to 2 hours prior to the start of Pan-HER infusion
- Antihistamine (H1 antagonist) equivalent to 25-50 mg IV diphenhydramine, approx. 0.5 hours prior to the start of Pan-HER infusion
- Antihistamine (H2) antagonist such as 50 mg IV ranitidine or 30 mg famotidine, approx. 0.5 hours prior to the start of Pan-HER infusion

Confidential Page 66 of 156

 Acetaminophen such as 1000 mg IV or PO (orally), approx. 0.5 hours prior to the start of Pan-HER infusion

In Part 2, if a patient is without evidence of IRRs after Cycle 2, the Investigator may choose to withdraw premedication on a patient-by-patient basis with subsequent dosing in order to determine whether such continued therapy is necessary in that patient. Where practical, it is recommended that withdrawal of premedication be done in a gradual fashion.

For those patients who experienced symptoms suggestive of an IRR after Cycle 1, consideration should be given to continuing premedication for at minimum 1 to 2 additional doses before any future attempt to withdraw.

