8.1 Baseline Characteristics / Eligibility Assessments

8.1.1 Signing of Informed Consent

Prior to any trial-related procedure, unless such testing was performed previously as part of the routine clinical management of the patient.

Screening

Note: Informed consent may be obtained outside the 14-day screening period prior to C1/D1, but is recommended to be obtained no earlier than 4 weeks prior to the planned C1/D1.

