9.2.3 Intensity

All referenced toxicity grading within this protocol will be according to the CTCAE v4.03. If the severity of an AE is not specifically graded by the CTCAE guidance document, the Investigator should use the general definitions of Grades 1 to 5 as per the following, and use his/her best medical judgment to describe the severity of the AE:

• Grade 1: Mild

Confidential Page 88 of 156

- Grade 2: Moderate
- Grade 3: Severe
- Grade 4: Life-threatening or disabling
- Grade 5: Death caused by the event

Changes in severity of AEs will be recorded.

Generally, an AE of Grade 4 or 5 qualifies for SAE reporting to the Sponsor or designee; however, the definition of Grade 4 does not necessarily always meet the regulatory definition of "life-threatening". As an example, a laboratory abnormality of Grade 4 does not need to be reported as an SAE, unless it meets one of the seriousness criteria in **Section 9.1.4**.

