3.2.4.2 Adverse Events

Definitions

An Adverse Event (AE) is any untoward medical occurrence in a patient or a clinical investigation patient administered a pharmaceutical product, and which does not necessarily have a causal relationship with this treatment. An AE can therefore be any unfavorable and unintended sign (including an abnormal laboratory finding), symptom, or disease temporally associated with the use of an IMP, whether or not considered related to the IMP.

Treatment-emergent AEs are events that occur on or after first dose of the study medication or a worsening in severity of a preexisting condition occurring on or after first dose of the study

PAREXEL International
Statistical Analysis Plan Template for Early Phase Studies

Symphogen A/S

Sym013-01

medication (a pre-existing is a condition that is present before the AE recording period starts and is noted on the medical history/physical examination form).

An IRR is defined as an AE occurring during the Pan-HER infusion and up to 2 hours after the end of infusion (EOI), which is assessed by the Investigator as possibly, probably, or related to Pan-HER; IRRs (Yes/No) will be captured in CRF.

AE duration will be derived as AE duration = (AE end date - AE onset date +1); in case of AE ongoing, the date of last contact with the patient will be used as AE for the scope of derive the AE duration.

An SAE is an AE that meets one or more of the following outcome criteria:

- Results in death
- Is life-threatening (patient is at immediate risk of death at the time of the event; it does not refer to an event which hypothetically might cause death if it was more severe)
- Requires in patient hospitalization (formal admission to a hospital for medical reasons) or prolongation of existing hospitalization
- Results in persistent or significant disability/incapacity
- Results in a congenital anomaly/birth defect
- Is medically important (Medically important events may not be immediately life-threatening or result in death or hospitalization but may jeopardize the patient or may require intervention to prevent one of the other outcomes listed in the definition above)

All AEs will be recorded from signing of informed consent for participation in the trial. The recording period ends at the time of the 1M FUP Visit.

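### As the SAP is written, an AE that starts between consent and first dose and then worsens on Pan-HER is not treatment-emergent, so the TEAE tables omit it unless the CRF opens a new record at each grade increase

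*SAP*

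**What the plan says.** SAP 3.2.4.2 gives two routes to treatment emergence: "Treatment-emergent AEs are events that occur on or after first dose of the study medication or a worsening in severity of a preexisting condition", with the worsening also dated on or after first dose. It then defines the term used in the second route: "a pre-existing is a condition that is present before the AE recording period starts and is noted on the medical history/physical examination form". The same section fixes the start of the recording period: "All AEs will be recorded from signing of informed consent for participation in the trial".

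Protocol 10.4.3.1 has a simpler rule. AEs arising after first treatment are TEAEs, AEs collected before dosing are not, and later worsening is not mentioned.

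On timing, Protocol 8.1.1 states "Informed consent may be obtained outside the 14-day screening period prior to C1/D1", and the footnotes to the assessment schedules in Protocol 5.3.5 say that consent is "recommended to be obtained no earlier than 4 weeks prior to the planned C1/D1". On grade changes, Protocol 9.2.3 says "Changes in severity of AEs will be recorded", and the SAP repeats this. Protocol 9.2.5 leaves the method of reporting changes in an ongoing AE to instructions that accompany the CRF pages.

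**The concern.** Treatment emergence should compare a patient's state before the first dose with the state after it. The worsening route instead takes consent as its reference point. Two patients with the same Grade 1 complaint on the day before dosing, both reaching Grade 3 after the infusion, are classified differently according to whether the complaint began the day before or the day after consent was signed.

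The definition of pre-existing matches Protocol 9.1.2, where it does a different job: it tells sites when a condition in the history has to be recorded as an AE. Reused to decide treatment emergence, it leaves a gap.

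It also sits badly with the SAP's own conventions. SAP 4.2 takes baseline as the last assessment before treatment, and SAP 4.11.4 measures laboratory grade shifts from that baseline. Safety and tolerability is the Part 1 primary objective. All nine AE summary tables are TEAE tables, including those for related events, serious events, worst grade and permanent discontinuation.

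**Working it through.** The plan gives no figure to reproduce on this point. The check traces cases through the rules.

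**Inputs**
- Route 1, onset at or after first dose; route 2, worsening of a pre-existing condition (SAP 3.2.4.2).
- Pre-existing: present before AE recording starts, and noted on the history or examination form (SAP 3.2.4.2).
- Recording starts at consent (SAP 3.2.4.2; Protocol 9.2.1).
- Partial dates are classified on the start date alone. An onset that is wholly unknown, or known only to the month and year (or only the year) of first dosing, is treated as a TEAE (SAP 3.2.4.2).
- Tables 14.3.1.1 to 14.3.1.9 are all restricted to TEAEs (SAP 6).
- Patients entered per cohort at Amendment 6: 1, 1, 4, 3, 7 and 3, total 19 (Protocol 3.2.4.1).

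**Trace: a Grade 1 event that becomes Grade 3 after the first infusion**

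| Start of the condition | Route 1 | Route 2 | In the TEAE tables? |
|---|---|---|---|
| Before consent, noted in history | no | yes | yes |
| Between consent and first dose, full date, grade change kept in the same record | no | no | no (0 of 9) |
| Same, but a new record is opened at the grade increase | yes, through the new onset date | not needed | yes |
| Same, but onset known only to the month and year of first dosing | yes, by the default rule | not needed | yes |

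The second row is the gap. Reading route 1 more broadly, so that a Grade 3 phase counts as occurring after first dose, does not close it. A separate worsening route would then be unnecessary, and the partial-date rules look only at the start date. Protocol 10.4.3.1 gives the same answer for that row, since the AE was collected before dosing.

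**Effect of one missed patient on a cohort's incidence**

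Change = 1/n, if the patient has no other event that qualifies for the same table row:
- n = 7: 1/7 = 14.3 percentage points
- n = 4: 1/4 = 25.0
- n = 3: 1/3 = 33.3
- n = 1: 1/1 = 100

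**Where the event would still appear (SAP 6)**
- Listing 16.2.7.2.1, all AEs.
- Listings 14.3.2.1 to 14.3.2.6, where applicable: SAEs, fatal AEs, permanent discontinuation, dose reduction, infusion interruption or stop, and deaths. These are titled as AE or death listings, and SAP 4.11.2 has non-TEAEs flagged in the SAE and death listings.
- Table 14.2.4.8, if it is a related Cycle 1 event meeting the DLT criteria. That table uses the DLT Analysis Set and has no TEAE filter.
- Tables 14.3.5.4 to 14.3.5.6, if it is a graded laboratory abnormality.

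**The case against.** The strongest reply is that the loss depends on a document we do not have. If the CRF instructions open a new record at each grade increase, every such worsening enters through route 1 and nothing is lost. SAP 4.11.2 provides for several occurrences of an event at different grades. That is compatible with separate records but does not establish them, since it may simply mean recurrences. This part of the reply stands as a condition on the finding. It does not remove the finding, because neither document states the convention and the tables should not rest on an unstated one.

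Second, the SAP already improves on the protocol by including a worsening route at all. The trial stopped during Part 1, the analyses are descriptive, and the report is abbreviated. All true, and it limits the importance. But all nine TEAE tables are among the outputs kept for the abbreviated report.

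A reader might go further in three ways that the documents do not support.
- **That on-drug worsening disappears from the safety reporting.** It does not. The primary endpoint, DLTs, has its own table, laboratory worsening has its own shift tables, and the listings keep the event.
- **That the exposure can be sized by multiplying the planned 34 patients by the two to four weeks before dosing.** Those are maximum or recommended limits, enrollment stopped early, some partial dates default to TEAE, and time at risk of onset does not say how many AEs begin, persist and then worsen.
- **That the gap is wider in the prophylaxis cohorts, distorting a comparison with and without prophylaxis.** Protocol 7.2.1 does place "Montelukast (selective leukotriene receptor antagonist) 10 mg PO daily × 7 prior to each Pan-HER infusion", but this does not lengthen the interval from consent to first dose. No AE attributed to that premedication is reported. Protocol 3.2.4.1 says it was already recommended for later patients without the mandatory regimen, and no formal comparison is planned.

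**Conclusion.** The concern holds in a limited form. The SAP states a rule that misclassifies one kind of event: a fully dated AE with onset between consent and first dose whose grade rises on treatment. The exposed outputs are Tables 14.3.1.1 to 14.3.1.9, and in practice mainly non-laboratory events.

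This assumes that grade changes are kept within the original AE record. If they are entered as new records, the effect is nil. The number of affected events cannot be derived from the documents. With a short window and a small Part 1 it is probably low, and it may be zero. The case for correcting it is that, in cohorts of the size reported at Amendment 6, a single omission is visible in the row concerned. Final cohort sizes are not given, so the percentages above are indicative. It is worth correcting, but it does not threaten the primary endpoint.

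**What to change.** In SAP 3.2.4.2, define a TEAE as an AE with onset on or after first dose, or any condition or AE already present before first dose, whether from the medical history or with onset after consent, whose CTCAE grade increases on or after first dose. Identify these cases from the severity changes that both documents say are recorded.

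Add one line stating how the CRF holds a grade change: as a new record with its own onset date, or within the existing record. If it is a new record, the counts do not change and the sentence simply makes the rule explicit.

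The cost is one SAP sentence, the line on CRF practice and a small programming step. No new data are needed, and a few more TEAEs may be counted.

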All referenced toxicity grading within this protocol will be according to the CTCAE v4.03. If the severity of an AE is not specifically graded by the CTCAE guidance document, the Investigator should use the general definitions of Grades 1 to 5 as per the following, and use his/her best medical judgment to describe the severity of the AE:

PAREXEL International
Statistical Analysis Plan Template for Early Phase Studies

Symphogen A/S

Sym013-01

- Grade 1: Mild
- Grade 2: Moderate
- Grade 3: Severe
- Grade 4: Life-threatening or disabling
- Grade 5: Death caused by the event

Changes in severity of AEs will be recorded.

AEs will be assessed for causal relationship to the IMP. The causal relationship of an AE to the IMP, Pan-HER, will be rated as follows:

- Not Related (The AE is not related to the IMP)
- Unlikely Related (The AE is considered not related to the IMP)
- Possibly Related (The AE might not be related, but possibility cannot be ruled out with certainty and therefore would be considered related)
- Probably Related (It has been determined with a high degree of certainty that the AE is associated with administration of IMP)
- Related (The AE is related to the IMP)

Outcome of the AE will be assessed utilizing one of the following terms:

- Recovered
- Recovered with sequelae (if recovered with sequelae, specify sequelae)
- Not recovered
- Fatal
- Unknown

PAREXEL International
Statistical Analysis Plan Template for Early Phase Studies

Symphogen A/S

Sym013-01

Handling of partial AE onset and end date

Any AEs with incomplete start and end dates will be treated as follows:

- Adverse events with completely unknown onset date will be considered as treatment-emergent; for the scope of AE duration derivation, these AE will be considered as occurred the day of first IMP infusion.
- Adverse events with unknown start day and month but with known start year will be considered:
 - as treatment-emergent if the start year coincides or is after the first dosing year; for the scope of AE duration derivation, these AE will be considered as occurred the day of first IMP infusion if the start year coincides with first dosing year, as occurred on 1st January otherwise (i.e. in case the start year is after the first dosing year)
 - as non-treatment emergent if start year is before the first dosing year; for the scope of AE duration derivation, these AE will be considered as occurred on 1st January.

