- Adverse events with unknown start day but with known start month and year will be considered:
 - as treatment-emergent if the start month and year coincide or are after the month and year of first dosing; for the scope of AE duration derivation, these AE will be considered as occurred the day of first IMP infusion if the start month and year coincides with first dosing month and year, as occurred on 1st day of the month otherwise (i.e. in case the month and year is after the month and year of first dosing)
 - as non-treatment emergent if start month and year is before the month and year of first dosing; for the scope of AE duration derivation, these AE will be considered as occurred on 1st day of the month.
- Adverse events with completely unknown end date will be considered as ended on the day of last contact with the patient).

PAREXEL International
Statistical Analysis Plan Template for Early Phase Studies

Symphogen A/S
Sym013-01

- Adverse events with unknown end day and month but with known end year:
 - if the AE end year is before the year of last contact with the patient, AE will be considered as ended on 31th December.
 - if the AE end year coincide with the year of last contact with the patient, AE will be considered as ended on day of last contact with the patient.
 - If AE end year is after the year of last contact with the patient, for the scope of derive the AE duration the date of last contact with the patient will be used as AE end date.
- Adverse events with unknown end day but known end month and end year:
 - if the AE end month and year are before the month and year of last contact with the patient, AE will be considered as ended on last day of the month.
 - if the AE end month and year are coinciding with the month and year of last contact with the patient, AE will be considered as ended on last day of last contact with the patient.
 - If AE end month and year are after the month and year of last contact with the patient, for the scope of derive the AE duration the date of last contact with the patient as AE end date.

Adverse events with completely or partial unknown start and end dates will be shown as not known (NK), for the respective unknown part, in the listings.

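### Three onset-imputation rules ignore the end date, so an adverse event known to have ended before the first infusion can be counted as treatment-emergent

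*SAP*

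**What the plan says.** All the rules are in SAP 3.2.4.2. The definition is "Treatment-emergent AEs are events that occur on or after first dose of the study medication", extended to pre-existing conditions that worsen from that time on. Recording starts before dosing: "All AEs will be recorded from signing of informed consent for participation in the trial".

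Three branches for missing onset dates lead to the same result:

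- **No onset date at all:** "Adverse events with completely unknown onset date will be considered as treatment-emergent". For the duration calculation, "these AE will be considered as occurred the day of first IMP infusion".
- **Year only:** "as treatment-emergent if the start year coincides or is after the first dosing year". Onset is set to first infusion if the year is the first-dosing year, and to 1 January if it is later.
- **Month and year only:** "as treatment-emergent if the start month and year coincide or are after the month and year of first dosing". Onset is set to first infusion if the month is the first-dosing month, and to the first of the month if it is later.

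Earlier partial dates go the other way: "as non-treatment emergent if start year is before the first dosing year", with a parallel rule for an earlier month. Duration is "AE duration = (AE end date - AE onset date +1"). A separate set of rules completes partial end dates. It does not feed back into TEAE status or into the imputed onset.

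**The concern.** None of the three branches asks whether the event was already over at first infusion. Consent precedes dosing: Protocol 8.1.1 allows it outside the 14-day screening period and only recommends that it be no more than 4 weeks before C1/D1. An event can therefore start and resolve before any drug is given and still be in the database. If its onset is missing in one of these three ways, the imputation rule makes it treatment-emergent, although under the SAP's definition it cannot be. It is also given an onset later than its own end.

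What is at stake is the accuracy of the all-cause TEAE tables, all of which SAP section 6 marks for the abbreviated study report, and of the flag that separates non-TEAEs in the serious adverse event listing. SAP 4.11.2 uses the same flag in the death listings. A fatal event in a treated patient cannot have ended before first infusion, so in practice the serious adverse event listing is the one exposed.

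**Working it through.** The plan gives no figure to reproduce, so the check applies the rules literally.

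**Inputs.** Let F be the day of first infusion. Imputed onset is F in all three branches, and duration is end − onset + 1 (both SAP 3.2.4.2). The known end date is F − k. The values of k are assumed, from 1 to 28 days, which covers the recommended 4-week consent window. Where calendar dates are needed, F is a hypothetical 20 July 2018.

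**Formula.** Duration = (F − k) − F + 1 = 1 − k.

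| k (days from end to first infusion) | Known end date | Status under the rule | Derived duration (days) |
|---|---|---|---|
| 1 | 19 July | TEAE | 0 |
| 2 | 18 July | TEAE | −1 |
| 5 | 15 July | TEAE | −4 |
| 14 | 6 July | TEAE | −13 |
| 28 | 22 June | TEAE | −27 |

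In the month-and-year branch the end date must lie in the first-dosing month, so with F on the 20th, k can be at most 19. The last row therefore applies only to the other two branches.

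**Partial end date.** Take no onset date, an end date known only as the year before dosing, and first infusion on 8 January. The SAP sets the end to 31 December, so k = 8 and duration = 1 − 8 = −7 days, again as a TEAE.

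**Controls.** An event with unknown onset that ends on F has duration 1, and one ending on F + 3 has duration 4. Both are properly TEAEs. With F on 20 July and an end on 15 July, a June 2018 onset without a day is set to 1 June. It is non-treatment-emergent with duration 45 days, so that branch works.

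**Comparison within the SAP.** Section 4.8 treats medications with missing dates as concomitant by default, but makes an exception when the dates show clearly that the medication stopped before first dose. The adverse event rules have the default without the exception.

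**Weight of one case.** Protocol 3.2.4.1 gives 1, 1, 4, 3, 7 and 3 patients in the cohorts entered by Amendment 6, a total of 19. One misclassified patient is 1/7 = 14%, 1/4 = 25% or 1/3 = 33% of a multi-patient cohort, all of a single-patient cohort, and 1/19 = 5% of the pooled column. These are upper limits for a preferred-term row. The tables count patients, so someone who also had the same event after dosing is in the row already.

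**The case against.** The strongest defence is that calling an unknown onset treatment-emergent is the cautious choice, because it over-counts toxicity and does not hide it. That holds when the end date is unknown or falls on or after first infusion. It does not hold when the end date shows that the event was over before dosing, since no uncertainty about treatment emergence is left to resolve.

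A second defence is that data checks would catch such cases. Protocol 14.7 provides validation checks and queries, and a missing start beside a pre-dose end is an obvious query. This lowers the expected number of cases but does not change the rule for those that remain unresolved.

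A reader might infer more than the documents support:

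- **That any partial onset becomes a TEAE at first infusion.** Earlier months and years are already non-treatment-emergent, and later ones are not set to first infusion.
- **That the related-TEAE tables are contaminated.** Those depend on the investigator's causality rating. Protocol 9.2.4 makes timing relative to dosing part of that rating, so an event that ended before any dose should be rated not related or unlikely related.
- **That the DLT or MTD evaluation is affected.** DLTs are collected in the CRF with their own criteria and observation period, and TEAE status plays no part.
- **That impossible durations will be summarised.** SAP section 6 lists no table or figure of adverse event duration. At most a listing shows the odd value, with the onset displayed as not known.

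**Conclusion.** Wrong as written, and minor. In three specific branches the SAP's imputation rule overrides its own TEAE definition for events known to have ended before first infusion, and gives them a duration of zero (k = 1) or less (k ≥ 2). Nothing else in the SAP or protocol overrides the rule.

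The effect is confined to the all-cause TEAE tables, the non-TEAE flag for serious events, and a derived duration that no table uses. Summary tables of other endpoints do not change. A case needs both a missing onset of the stated kind and an end date, or known part of one, that places the end before first infusion. The documents do not say how many such events exist. That few are expected is a judgement based on the short window between consent and dosing and on the query process.

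**What to change.** Add one exception to three branches of SAP 3.2.4.2 only: completely unknown onset, year-only onset in the first-dosing year, and month-and-year onset in the first-dosing month. Suggested wording: *unless the end date, or its known part, shows that the AE ended before the first infusion, in which case the AE is non-treatment-emergent, its onset is not imputed to first infusion, and its duration is left missing.*

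The branches for earlier and later partial dates need no change. Leaving duration missing avoids inventing an onset date and costs nothing, because duration is not summarised. The logic mirrors the stop-date check in SAP 4.8.

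The cost is one SAP clause and one programming condition. It needs no new data and changes no design element, and events ending on or after first infusion keep their status and duration. SAP section 1 already provides for revisions to be documented in the study report.
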